## 2.1 Table 1: Schedule of Events

Study Phase	PRE-SCREENING	TREATMENT PROCEDURES						END OF STUDY		
		INFORMED CONSENT PROCEDURES	SCREENING PROCEDURES	RUN-IN PROCEDURES	RANDOMIZATION PROCEDURES	BASELINE PROCEDURES	Post-treatment (0 hours) + 30 minutes	Post-treatment (2 hours) ± 30 minutes	Post-treatment (24 hours) ± 1 hour	Post-treatment (48 hours) ± 2 hours
Event/Timeline		~3 weeks	~1 week	~6 weeks	~1 week	Day 0				
Pre-screening questionnaire	X						Day 0	Day 0	Day 1	Day 2
Electronic Informed Consent		X								
Screening questionnaire			X							
Medical History & Demographics			X							
Concomitant medications review 				X						
Eligibility assessment			X	X 						
Training				X 	X 					
Migraine run-in eDiary (28 days)				X						
Participant check-in				X						
Eligibility confirmation				X						
Randomization					X					
Device shipment					X					
Head pain severity score 						X				
Most Bothersome Symptom 						X				
Nausea severity score 						X				

	COT-004 CALM 3				
	Page 21 of 54	Version 3.0			

Photosensitivity severity score 					X		X	X	X	X	
Phonosensitivity severity score 					X		X	X	X	X	
Rescue medication use 							X	X	X	X	
Adverse Event review and evaluation					X		X				
Device tolerability and user experience questionnaire								X	X 		
Return of test article											X

Eligibility Confirmation will include review of relevant medical records to confirm diagnosis of migraine in participants who pass the E-Diary.

Training will cover how to complete the migraine eDiary.

Training will cover set-up and use of the Mi-Helper Device.

Based on a 4-point Verbal Rating Scale (VRS).

Participants will be advised against using rescue medication until collection of the Migraine Symptom Questionnaire at 2 hours post-treatment, however, the use of rescue medication prior to 2 hours post-treatment will be captured as a treatment failure, and will be assigned a status of no reduction

Select user experience questions will be repeated as a part of 24-hour post-treatment assessment.

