### **Treatment Procedures (48 hours)**

Participants will be instructed to use the Mi-Helper device once their migraine head pain has reached at least mild intensity. This will be determined by their response to the question about their head pain within the Study App. Participants will be instructed to use the Mi-Helper within 1 hour from the time of migraine head pain onset.

Once the migraine headache score is recorded as being mild to severe (score of 1 to 3 recorded on the 4-point VRS scale) and the participant has confirmed that they have not used any acute migraine medications in the last 48 hours, the Study App will instruct the participant to initiate treatment with the Mi-Helper device and dose treatment (active or sham) for a total of 15 minutes based on their group allocation. Participants will be advised against using any rescue medication until collection of the Migraine Symptom Questionnaire at 2 hours post-treatment with the Mi-Helper device. However, if participants do need to administer rescue treatment after administering treatment with Mi-Helper, they will need to report this using the 'Rescue Medication Form' within the Study App. Use of rescue medication within 2 hours of treatment will be considered a treatment failure. In the instance that abortive treatments have been used 48-hours prior to the start of treatment or the time of onset of migraine head pain exceeds 1 hour, the participant will need to wait until their next migraine episode of at least mild intensity, to use the device.

Participants will be instructed that they may stop treatment if they are unable to tolerate it by moving the nebulizer away from their nose, and report this within the Study App.

Participants will be required to respond to questions about their head pain, nausea, photosensitivity, phonosensitivity, and the most bothersome symptom (MBS) within the Study App immediately post-treatment and then at 2 hours, 24 hours and 48 hours post-treatment.

At 2 hours post-treatment, participants will also be required to respond to questions about the device tolerability and user experience questionnaire. Select user experience questions will be repeated in the 24-hour assessment.

Participants can report any changes in their health through the Study App while participating in this study.

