If migraine symptoms have not resolved, participants will be able to use rescue medication between the 2-to-48-hour period after using the device. Participants will be instructed to report rescue medication use in the 'Rescue Medication Form' within the Study App. This form will be

available for participant use during the entire post-treatment period through the Study App and will not be timepoint bound.

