## 7.4 Concomitant Diets, Treatments, and Medications

Participants are prohibited from using their acute migraine medications within 48 hours prior to using the Mi-Helper device. Acute medication may include over-the-counter medications like non-steroidal anti-inflammatory drugs (i.e., aspirin or ibuprofen) and acetaminophen; prescription medications like triptans (i.e., sumatriptan, zolmitriptan, etc.), gepants

(ubrogepant, Rimegepant,etc.), antiemetics (metoclopramide, prochlorperazine, or promethazine); or another medical neuromodulation device like Cefaly®.

Participants should continue to take any prescribed migraine preventive medications as instructed by their physician.

Participants may use rescue medication(s) after administering treatment with Mi-Helper, however, rescue medication used within 2 hours of treatment will be considered a treatment failure. Participants will be advised against using their rescue medication until collection of the Migraine Symptom Questionnaire at 2 hours post-treatment. An ad hoc rescue medication form will be available on the Study App's dashboard after administration of study treatment (control or active) for participants to fill out if they decide to use rescue medication(s) prior to collection of the Migraine Symptom Questionnaire at 2-hours post-treatment. They will be asked about their migraine symptoms when they fill out the ad hoc rescue medication form.

No dietary restrictions are required for this protocol.

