2hr Pain Freedom	Primary Efficacy Endpoint	Baseline Migraine Symptom Questionnaire 2-hour Post Treatment Migraine Symptom Questionnaire	n% Achieved if Head Pain changes from Severe, Moderate, or Mild at baseline to None at 2hrs post-treatment.
2hr MBS Freedom	Secondary Efficacy Endpoint	Baseline Migraine Symptom Questionnaire 2-hour Post Treatment Migraine Symptom Questionnaire	n% Achieved if MBS changes from Severe, Moderate, or Mild at baseline to None at 2hrs post-treatment.
2-24hr Sustained Pain Freedom	Secondary Efficacy Endpoint	Episodic Rescue Medication Questionnaire Baseline Migraine Symptom Questionnaire 2-hour Post Treatment Migraine Symptom Questionnaire 24-hour Post Treatment Migraine Symptom Questionnaire	n% Achieved if Pain Freedom is sustained from 2 hours post-treatment until 24 hours with no administration of rescue medication and with no recurrence of a mild/moderate/severe headache.
2hr Pain Relief	Secondary Efficacy Endpoint	Baseline Migraine Symptom Questionnaire 2-hour Post Treatment Migraine Symptom Questionnaire	n% Achieved if Head Pain changes from Severe or Moderate at baseline to Mild or None at 2 hours post-treatment, OR if Head Pain changes from Mild at baseline to None at 2 hours post-treatment.
Global Impression of Acute Treatment Effect	Secondary Efficacy Endpoint	24-Hour Post Treatment User Experience Questionnaire	Patient Global Impression of Change measure
Rescue Medication use 0-2hrs Post Treatment	Exploratory Endpoint	Episodic Rescue Medication Questionnaire	

		2-hour Post Treatment Migraine Symptom Questionnaire	
0hr Pain Freedom	Exploratory Endpoint	Baseline Migraine Symptom Questionnaire Immediate Post Treatment Migraine Symptom Questionnaire	n% Achieved if Head Pain changes from Severe, Moderate, or Mild at baseline to None immediately post-treatment.
0hr Pain Relief	Exploratory Endpoint	Baseline Migraine Symptom Questionnaire Immediate Post Treatment Migraine Symptom Questionnaire	n% Achieved if Head Pain changes from Severe or Moderate at baseline to Mild or None immediately post-treatment, OR if Head Pain changes from Mild at baseline to None immediately post-treatment.

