8.1. Primary Efficacy Analysis

- Pain freedom at 2 hours is defined as the reduction in head pain to “none”, i.e., from severe, moderate, or mild head pain to none. Pain will be rated on a scale from 0 to 3, where 0 is no pain and 3 is severe pain. Pain freedom will compare the active arm to the sham arm using a Chi-squared test.
- Use of rescue medication prior to 2 hours post treatment completion will be considered a failure for this endpoint (i.e., patient will be assigned the status of no reduction).
- A sensitivity analysis of the primary endpoint will be performed to assess the impact of missing data on the study outcome. This will be done on the ITT analysis set, where missing 2-hour pain assessment is considered not to be pain free.

- Subgroup analyses will be conducted to evaluate whether treatment effects on the primary endpoint differ by gender, age group, use of preventive medications, and baseline headache severity. These analyses will help assess the generalizability of the treatment effect across diverse patient populations.

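### The primary endpoint fails rescue medication only before 2:00 hours, but accepts the pain score until 2:30, so a score of none given after rescue can count as a success in either arm

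*SAP*

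**What the plan says.** **Failure rule.** SAP 8.1 reads "Use of rescue medication prior to 2 hours post treatment completion will be considered a failure for this endpoint". SAP 3.2.1 and the protocol (synopsis, section 4 and 11.6.1) use the same cut-off. The footnote to the schedule of events repeats it: "the use of rescue medication prior to 2 hours post-treatment will be captured as a treatment failure".

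**Scoring window.** The schedule of events (protocol 2.1) sets the assessment at "Post-treatment (2 hours) ± 30 minutes", so a valid score may be given from 1:30 to 2:30 after treatment completion.

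**Instructions on rescue.** Protocol section 5, Treatment Procedures, says: "Participants will be advised against using any rescue medication until collection of the Migraine Symptom Questionnaire at 2 hours post-treatment with the Mi-Helper device". The end of the same subsection says that, if symptoms have not resolved, "participants will be able to use rescue medication between the 2-to-48-hour period after using the device". The first statement is tied to collection of the score, the second to the clock.

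**Derivation.** SAP 7.1, Table 1, defines 2hr Pain Freedom as "Achieved if Head Pain changes from Severe, Moderate, or Mild at baseline to None at 2hrs post-treatment". Its listed sources are the baseline and 2-hour symptom questionnaires. For sustained pain freedom, the same table also lists the rescue medication questionnaire.

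**Rescue form.** Protocol 7.4 provides an ad hoc form for rescue taken before the 2-hour questionnaire is collected, and adds: "They will be asked about their migraine symptoms when they fill out the ad hoc rescue medication form".

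**The concern.** The failure rule follows the clock, while the outcome is a score that may come up to 30 minutes after the clock has run out. For those 30 minutes, rescue is not a failure and the score is still open. A score of none given after rescue would be credited to the assigned treatment, active or sham, in the trial's primary endpoint.

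Two things are at stake. One is the meaning of the endpoint, which is intended as pain freedom without help from other medication. The other is that the programmer would have to decide how to classify a score time-stamped after rescue. Unless the plan states it, that decision is made once the data exist.

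**Working it through.** **Step 1. Timing (hours:minutes after treatment completion).**

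| Interval | Rescue here is a failure? | 2-hour score accepted? |
|---|---|---|
| 0:00 to 1:30 | yes | no |
| 1:30 to 2:00 | yes | yes |
| 2:00 to 2:30 | no | yes |

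The gap is the last row: 2:30 − 2:00 = 30 minutes. Rescue at 2:05 with none at 2:25 meets the written definition of success.

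**Step 2. Does anything else close the gap?**
- The advice to wait for the questionnaire is not a scoring rule.
- The mITT set requires device use and the baseline and 2-hour scores. It has no rescue condition.
- The protocol's per-protocol set uses the same 2-hour cut-off, and the SAP's per-protocol set states no rescue condition.
- The ITT sensitivity analysis deals only with missing 2-hour scores.
- Symptoms are asked on the rescue form, but no text lets that report replace a later 2-hour score.

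**Step 3. The plan's own figure.** The inputs from SAP section 5 are 41% versus 16%, two-sided 5%, 80% power, two-tailed Fisher's exact test and 58 per arm. Exact enumeration of Fisher's test at 58 per arm gives power of 81.7%, which agrees with the plan. The planned primary test is the Pearson chi-squared test; its exact power at the same inputs is 86.4%. The scenarios start from that value.

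**Step 4. Size, under stated assumptions.** The documents give no rate for this event, so the counts below are illustrations. Let k be the expected number of sham cases.
- One case moves an arm by 1/58 = 1.7 points.
- Expected non-responders: sham 0.84 × 58 = 48.7; active 0.59 × 58 = 34.2.
- Equal conversion: share s = k/48.7. The sham rate becomes 0.16 + k/58 and the active rate 0.41 + 0.59s. Each sham case comes with 34.2/48.7 = 0.70 active cases.
- Sham only (extreme): the active rate stays at 41%.

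| Sham cases k | Equal conversion: rates | Difference (points) | Power | Sham only: rates | Power |
|---|---|---|---|---|---|
| 0 | 41.0% v 16.0% | 25.0 | 86.4% | 41.0% v 16.0% | 86.4% |
| 1 | 42.2% v 17.7% | 24.5 | 83.7% | 41.0% v 17.7% | 80.2% |
| 2 | 43.4% v 19.4% | 24.0 | 80.9% | 41.0% v 19.4% | 72.9% |
| 3 | 44.6% v 21.2% | 23.5 | 77.9% | 41.0% v 21.2% | 64.6% |

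**Step 5. The opposite extreme.** Suppose there is no true effect (16% in both arms) and two cases on active only. The active rate is 0.16 + 2/58 = 19.4%. The two-sided rejection rate rises from 5.2% to 8.0%.

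**The case against.** The strongest reply is that cases will be rare. One requires that no score has been given by 2:00, that rescue is taken after 2:00 despite the advice to wait, that the score follows by 2:30, and that pain falls to none in under 30 minutes. Partial relief is not enough. This stands, and zero cases is plausible.

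It can also be said that the plan partly handles the case. The rescue form would help to identify it. Sustained pain freedom from 2 to 24 hours requires no rescue, so such a participant fails there. The per-protocol set could drop the participant if the event were classed as a major deviation. These points stand only in part. No rule uses the form's symptom report, sustained pain freedom is a secondary endpoint that cannot correct the primary, and nothing in the documents classes the event as a major deviation.

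Two stronger readings are tempting. A reader might infer that the gap favours the device. The documents do not support that: the rule is the same in both arms, and if sham participants take rescue more often the difference shrinks. A reader might also take the sham-only losses, down to 64.6%, as the expected cost. They hold only if no active participant is ever affected, which is an extreme. With equal conversion, power stays above the planned 80% for one or two sham cases.

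**Conclusion.** The concern holds. The failure cut-off and the scoring window of the primary endpoint do not match, and no scoring rule, analysis set or sensitivity analysis corrects the mismatch. This is a rule that gives an unintended result, not a missing detail.

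Its likely effect is small. The direction of bias is unknown and the number of cases is not given. The figures rest on 58 evaluable per arm, the plan's 41% and 16%, and assumed counts. On those terms, one to three sham cases with equal conversion cost 86.4 − 83.7 = 2.7 to 86.4 − 77.9 = 8.5 points of power. The one-sided extremes run from 64.6% power (three cases, sham only) to an 8.0% rejection rate under no effect (two cases, active only). The planned sample size is not affected. The change is worth making because it is cheap and removes a classification decision that would otherwise be made after the data exist.

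**What to change.** - In SAP 3.2.1 and 8.1, and in the protocol synopsis, section 4 and 11.6.1, state: rescue medication taken before 2 hours post treatment completion, or before the time stamp of the 2-hour pain score, whichever is later, is a failure. Taking the later of the two leaves every current failure a failure, including rescue taken after an early score but before 2:00.
- In SAP Table 1, add the rescue condition to 2hr Pain Freedom and list the rescue medication questionnaire as a data source.
- Confirm that the rescue form records the time of intake, not only the time of entry.
- The two statements in protocol section 5 on rescue, one tied to the questionnaire and one to the clock, must be reconciled. The scoring clause does not depend on how that is done and does not change when participants may take rescue.

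The cost is one clause in each place and one table entry. The downside is that a few successes may be reclassified as failures. Whether freedom from the most bothersome symptom and pain relief at 2 hours should also carry a rescue-failure rule is a separate point, since their definitions now state none.

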8.2. Secondary Efficacy Analysis

- A hierarchical testing approach will be employed using a fixed-sequence procedure to control type I error due to multiple endpoint testing. The primary endpoint will first be tested and only if $p < 0.05$, will the secondary endpoints be tested. Testing will proceed sequentially, and each endpoint must achieve statistical significance at the 0.05 level to proceed to the next endpoint. If any endpoint in the sequence fails to achieve significance, all subsequent endpoints will not be formally tested and will be considered exploratory.
- The secondary efficacy variables will be summarized by a count and percentage and compared with a chi-squared test. Analysis of secondary endpoints will follow the hierarchical testing approach outlined above to control type I error due to multiple endpoints.
- Global Impression of Treatment Effect will also be summarized by descriptive statistics per treatment group and compared between the groups with a t-test.

8.3. Exploratory Efficacy Analyses

- The exploratory variables will be summarized by a count and percentage and compared with a chi-squared test
- Frequency of use of rescue medications will be summarized by descriptive statistics per treatment group and compared between the groups with a t-test.

9. SAFETY ANALYSIS

The primary safety outcome is the incidence of adverse events related to the study device for 48 hours post treatment completion.

Safety of the Mi-Helper device measured by incidence of adverse events with groups compared using Fisher's exact test for proportions.

AEs will be categorized as related, probable, possible, unlikely, or unrelated prior to database lock. The number of AEs/SAEs and number of participants with AEs/SAEs will be listed and tabulated.

Treatment tolerability will be compared between the study groups. The number and percent of subjects who fail to complete the study treatment due to discomfort and the number and percent of subjects who fail to complete the study because of Adverse Events will be presented as well.

- 9.1. Adverse Events
- 9.2. Deaths, Serious Adverse Events and other Significant Adverse Events
- 9.3. Pregnancies

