### 11.7 Safety Analysis

The primary safety outcome is the incidence of adverse events related to the study device for 48 hours post treatment completion.

AEs will be categorized as related, probable, possible, unlikely, or unrelated prior to database lock. The number of AEs/SAEs and number of participants with AEs/SAEs will be listed and tabulated.

Adverse event rates will be compared between the study groups with a Fisher's exact test.

Treatment tolerability will be compared between the study groups. The number and percentage of subjects who fail to complete the study treatment due to discomfort and the number and percentage of subjects who fail to complete the study because of Adverse Events will be presented as well.

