3. STUDY OBJECTIVES AND ENDPOINTS

3.1. Study Objectives

3.1.1. Primary Objective

- To determine the safety and efficacy of one dose of Mi-Helper therapy compared to sham for the acute treatment of a single migraine attack.

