8. EFFICACY ANALYSIS

The Pearson Chi-squared test will be used to compare randomized arms with regards to primary and secondary endpoints. Logistic regression modeling will estimate odds ratios and 95% confidence intervals for pain relief/freedom endpoints to compare the two groups. The absolute difference in rates of freedom from pain will be estimated with 95% confidence intervals. Binomial exact 95% confidence intervals will be constructed for the incidence of primary and secondary endpoints within each group.

All statistical analyses will be performed using Stata software (version 19, StataCorp LLC, College Station, Texas).

Deviations from the planned analysis will be described, with proper justification, in the clinical study report.

Type I Error: The overall significance level for this study is 5% using two-tailed tests

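### Safety versus sham is part of the primary objective, but the only planned between-arm inference for adverse events is a Fisher p-value, with no estimate or interval for the difference.

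*SAP*

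**What the plan says.** SAP 3.1.1 sets the primary objective as "To determine the safety and efficacy of one dose of Mi-Helper therapy compared to sham", and Protocol section 4 has the same objective. SAP section 9 then defines the safety outcome: "The primary safety outcome is the incidence of adverse events related to the study device for 48 hours post treatment completion".

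For the comparison between arms, SAP section 9 has "Safety of the Mi-Helper device measured by incidence of adverse events with groups compared using" Fisher's exact test. Protocol 11.7 has "Adverse event rates will be compared between the study groups", again with Fisher's exact test. Both sections also plan descriptive output: "The number of AEs/SAEs and number of participants with AEs/SAEs will be listed and tabulated". They add a tolerability comparison, with numbers and percentages stopping treatment because of discomfort or leaving the study because of AEs.

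The efficacy side gets more. SAP section 8 states "The absolute difference in rates of freedom from pain will be estimated with 95% confidence intervals", adds odds ratios for the pain endpoints, and says "Binomial exact 95% confidence intervals will be constructed for the incidence of primary and secondary endpoints within each group". Protocol 11.4 has equivalent text. Neither document gives a risk difference, risk ratio, interval, margin or power statement for AEs.

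**The concern.** A p-value from a test of no difference does not tell the reader how large an increase in AEs the data still allow, and for a safety objective that is the main question. The trial was sized for 2-hour pain freedom, not for AEs. If AE rates are low, a non-significant Fisher test is the more probable result even when the active arm has a materially higher rate. A report that follows the plan to the letter could give two percentages and a non-significant p-value, and leave readers to work out the precision themselves. The plan already treats pain freedom better than this, so the gap is one of consistency as well as of method.

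**Working it through.** **1. The plan's own figure.** Inputs from SAP section 5: 41% v 16% pain-free at 2 hours, two-tailed Fisher test, 5% level, 80% power, 25% dropout.
- The continuity-corrected two-proportion formula gives 58 per arm.
- Exact enumeration of the two-sided Fisher test at 58 per arm gives 81.7% power.
- Dropout: 58 / 0.75 = 77.3, rounded up to 78 per arm, so 156 in total.

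The stated sample size reproduces. It concerns efficacy only.

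**2. Denominator for safety.** SAP 6.1 makes ITT (all randomized) the main safety set, so 78 per arm.

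**3. AE rates.** The documents give no AE rate for 10 LPM or sham and assume none for this trial. All rates below are assumptions, shown as a range.

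**4. Power of the planned Fisher test.** Power is the sum, over all pairs (a, b) with two-sided Fisher p ≤ 0.05, of Bin(a; n, p1) × Bin(b; n, p2). The level follows SAP section 8: "The overall significance level for this study is 5% using two-tailed tests".

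| Assumed AE rate, active v sham | Power, 78 per arm | Power, 58 per arm |
|---|---|---|
| 10% v 5% | 14% | 8% |
| 20% v 10% | 34% | 24% |
| 15% v 5% | 47% | 31% |
| 30% v 10% | 86% | 72% |

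The 58-per-arm column is for reference, as the plan's evaluable number. For a threefold ratio, power passes 50% at a sham rate of about 5.3% with 78 per arm (7.1% with 58), and passes 80% at about 9.0% (11.4% with 58).

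**5. Dilution.** ITT includes people who never use the device. If 25% of each arm were untreated and had no device-related AEs, 15% v 5% among treated participants would become 0.75 × 15% = 11.25% v 0.75 × 5% = 3.75%. Power at 78 per arm then falls from 47% to 32%.

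**6. What an interval would add.** The Newcombe interval combines the two single-arm Wilson intervals (l, u):

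lower = d − √[(p1 − l1)² + (u2 − p2)²], upper = d + √[(u1 − p1)² + (p2 − l2)²].

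*Illustration A, 9/78 v 3/78.*
- p1 = 11.54%, Wilson 6.19% to 20.50%.
- p2 = 3.85%, Wilson 1.32% to 10.71%.
- d = 7.69 points.
- Lower = 7.69 − √(5.35² + 6.86²) = 7.69 − 8.70 = −1.0.
- Upper = 7.69 + √(8.96² + 2.53²) = 7.69 + 9.31 = 17.0.
- Fisher p = 0.13.

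*Illustration B, 3/78 v 3/78.*
- d = 0, and each half-width is √(6.86² + 2.53²) = 7.31, so the interval is −7.3 to +7.3 points.
- Fisher p = 1.0.

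In A the p-value alone says no significant difference, while the data allow an increase of up to 17 points. In B the p-value is 1.0, and the data still allow 7.3 points either way.

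**The case against.** The strongest reply is that the plan does not rest on the p-value. Counts of events and of affected participants will be tabulated, and SAP 7.1 has tables split by treatment group. Stopping because of discomfort or AEs will be shown too. No margin, success claim or decision rule is attached to the Fisher test, and the plan nowhere says that non-significance will count as evidence of safety. All of this stands.

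A reader might therefore infer too much: that safety is judged by a p-value alone, that a tripled AE rate could be hidden, or that the trial cannot answer its safety question. The documents do not support these readings. An observed 9 v 3 would be plain in the tables, and anyone could compute an interval from the counts. Nor is non-significance generally the likely result. No AE rate is stated, and a tripling from 10% to 30% would be detected with 86% power at 78 per arm.

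Two further points have some weight. Protocol 11.4 is not confined to efficacy. Its exact within-group intervals for primary and secondary endpoints could be read as covering the safety endpoint, which Protocol section 4 lists in the primary row. If so, per-arm precision is already planned, but the difference from sham still is not. Also, SAP 11.1 leaves table content to TLF shells that are not among the documents, so an interval may be intended there. It should still be specified in the SAP.

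**Conclusion.** The point holds in a limited form. Safety against sham belongs to the primary objective, yet the only planned between-arm inference for AEs is a Fisher p-value, while freedom from pain has an absolute difference with a 95% interval. The missing item is the estimate and precision of the AE difference.

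How much this matters depends on AE rates that the documents do not give. With all 78 per arm in the safety set, power runs from 14% to 86% over the assumed scenarios. Where rates are low (for a threefold ratio, a sham rate below about 5%), a non-significant result is more likely than not and says little. Where rates are higher, the test is reasonably sensitive. Untreated participants in the ITT set would lower the power. In every scenario the interval gives information that the p-value does not. This is a cheap improvement to the analysis plan, not a flaw that invalidates the trial.

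**What to change.** In SAP section 9 and Protocol 11.7:
- Make the risk difference, active minus sham, with a 95% score-type interval (Newcombe or Miettinen-Nurminen, named in advance) the main between-arm result for device-related AEs to 48 hours.
- Give the same estimate and interval for stopping treatment because of discomfort.
- Keep Fisher's exact test as descriptive, and state that a non-significant result will not be read as evidence of safety.

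The cost is a few sentences and some table columns. It needs no extra participants or data and uses no alpha. The downside for the sponsor is that the interval will show openly how little a trial of this size can rule out.
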